Cover Page for Protocol

Official Study Title:	Labor and Delivery Doula Program to Reduce Perinatal Morbidity and Mortality in Kansas
NCT Number:	NCT07157059
Document Date:	10/03/2023

University of Kansas Medical Center
RESEARCH PROTOCOL INVOLVING HUMAN SUBJECTS

Version date: 03 Oct 2023

Principal Investigator: [name] [name], M.D.

Study Title: Labor and Delivery Doula Program to Reduce Perinatal Morbidity and Mortality in Kansas

Co- Investigator(s): [name], M.D., [name] L [name]., [name] [name], Ph.D., [name], M.D.

I. Purpose, Background and Rationale

A. Aim and Hypotheses

1. Black-birthing people are at increased risk of adverse outcomes during pregnancy and childbirth compared to their White counterparts. The aim of this study is to determine if Doula enhanced care can improve the perceived communication and quality of maternal care among Black-birthing people compared to routine pregnancy care, to minimize adverse perinatal outcomes in Black-birthing people in the long-term.
2. Hypothesis: Patients who receive Doula enhanced care will have higher satisfaction due to improved perceived communication and quality of care. Doula enhanced care will lower instances of cesarean delivery, preterm birth, and postpartum depression rates, and improved rates of breastfeeding for Black-birthing people.

B. Background and Significance

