3. Study Significance: This study will hopefully provide evidence that Doula enhanced care improves the quality of the healthcare process through improved communication and satisfaction for Black birthing people (primary outcome). In addition, we hope to show Doula enhanced care will improve specific disparities for Black birthing people including cesarean delivery, preterm birth, postpartum depression, and breastfeeding rates (our secondary outcomes). If our study is successful in showing these improvements in birth equity, we will submit an NIH (National Institutes of Health) R01 proposal to conduct a large-scale study on Doula enhanced care to improve the quality of health care for all birthing people. Black mothers have increased risk of cesarean delivery, preterm birth, postpartum depression, and lower rates of breast feeding (1). Poor pregnancy outcomes among Black-birthing people are multifactorial. Doula support during pregnancy and childbirth is associated with improved engagement and communication with the healthcare team, increased satisfactions with the birth experience, and decreased maternal stress (2,3). These factors may explain why Doula support has also proven to lower rates of cesarean delivery, preterm birth, postpartum depression and improve breast feeding rates (3,4,5).
4. Literature Review: Several studies suggest doula services help address birth inequities. First, doula services for pregnant people at risk of poor birth outcomes because of low-income or racial diversity may help disrupt influence of social determinants as predisposing factors for health during pregnancy and childbirth. Second, doula supported people have shortened labor and a decreased need for cesarian deliveries and other high-

risk procedures. They also rate childbirth as less difficult and painful than those without support. This can lead to lowering costs of care for pre-term and cesarian sections. Furthermore, doula services may also facilitate a higher rate of breast feeding.

C. Rationale

1. Based on associations between Doula enhanced care and reductions in cesarean delivery and preterm birth, coverage reimbursement for Doula services have proven to be cost-effective (6). However, there are significant socioeconomic, structural, and systemic barriers to Doula access, often preventing the most vulnerable patients from receiving Doula enhanced services.

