2. By better understanding if Doula enhanced care improves communication and quality of maternal care, we can begin to understand how to improve maternal care for Black birthing people. Also, by having Doula enhanced care available, we might reduce the chances of cesarean delivery and preterm birth and increase the likelihood of breastfeeding.

II. Research Plan and Design

A. Study Objectives:

1. The primary objective of the study is to demonstrate improved perceived communication and quality of maternal care among Black birthing people with Doula enhanced care compared to routine pregnancy care at the University of Kansas Health System. This study's primary outcome is to provide evidence that Doula enhanced care improves communication and satisfaction for Black-birthing people by improving the quality of healthcare with the addition of Doula enhancement to the health care team. In addition, the secondary outcome is to show how Doula enhanced care will improve specific disparities between Black birthing people and their White counterparts, including cesarean delivery, preterm birth, postpartum depression, and breastfeeding rates.

B. Study Type and Design:

This study will be an interventional randomized control trial that will have a control group and an experimental group. These groups will be randomly assigned at the patient's enrollment into the study.

C. Sample size, statistical methods, and power calculation

1. Two test Run patients will receive Doula Care from [name]. This will consist of two prenatal visits.
2. Randomization will be 1:1 and will stop after reaching our desired sample size of forty total patients. Forty patients will be enrolled in the study. Twenty patients will receive Doula enhanced care and Twenty patients will receive routine pregnancy care.

D. Subject Criteria (See Vulnerable Populations appendix, if applicable):

1. Inclusion criteria:

- a. Black birthing people receiving prenatal care with planned delivery at University of Kansas Health System between the ages of 16 and 50 years old.
 - i. Parental consent is not required for minors less than 18 years old because this study is directly related to their pregnancy.
- b. A positive social determinants of health screen.

- c. Patients must have an estimated gestational age of at least 14 weeks, but less than 28 weeks (27.6) when enrolled in the study.

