1. Laboratory tests: No lab tests will be needed for this study. Study Procedures: We plan to use RedCap electronic data collection tool provided by the University of Kansas Health System. A chart review will be performed to obtain maternal demographic information and secondary outcomes including maternal age, gravity/parity, gestational age at delivery, indication for delivery, mode of delivery, neonatal birthweight, presence of maternal comorbidities such as hypertension, preeclampsia, diabetes, fetal growth restriction, and complications of labor including protracted labor, chorioamnionitis, shoulder dystocia, perineal lacerations, and postpartum hemorrhage. Breastfeeding status at time of postpartum visit will also be collected. This information will be recorded in the RedCap data collection tool. A mixed-methods survey, including eight qualitative and four open ended questions, will be administered by the research coordinator at the postpartum follow-up for both groups. Quantitative questions will assess prenatal, labor and delivery, and postpartum perceived quality of care and satisfaction. Questions will aim to evaluate healthcare communication and perceived quality and respectfulness of care. Qualitative questions will provide the opportunity to comment on the aspect of care that improved the quality of care and contributed to the satisfaction of care. Qualitative responses will be coded to identify common themes. Participants randomized to "Routine Pregnancy Care" will continue to receive routine prenatal care at The University of Kansas and routine pregnancy care during the labor and delivery hospitalization. All postpartum patients at the University of Kansas Health System are screened for postpartum depression using the Edinburgh scale on the day of discharge and at 2 weeks following their delivery by a phone call from a nurse. This will be done for both groups per routine protocol at the University of Kansas Health System. All routine care patients will complete the quantitative survey, have a postpartum follow-up appointment with a provider within 2-6 weeks, and their EHR (Electronic Health Record) will be reviewed to assess the study secondary outcomes. Participants randomized to "Doula Enhanced Care"

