 - b. Data/events that will be reviewed **N/A**
 - c. Frequency of review **N/A**
 - d. Types of analyses to be performed **N/A**
2. Safety-related triggers that would cause the PI (Principal Investigator) to stop or alter the study: The study does not intervene with routine pregnancy care, minimal risk only.

3. The study does not intervene with routine pregnancy care, minimal risk only.
4. The study does not intervene with routine pregnancy care, minimal risk only.

III. Subject Participation

A. Recruitment:

1. Recruiting for the study will be done in the waiting rooms, clinic exam rooms, and via telephone at the University of Kansas Medical System.
2. The study team will screen for black patients presenting to the University of Kansas Health System Department of OBGYN for prenatal care using the "Social Determinants of Health" screening tool in Epic, the electronic medical record (EMR), utilized in the outpatient settings. Patients with one or more positive question in any of the following areas equals positive social determinants of health screen: tobacco use, alcohol use, financial resource strain, transportation needs, social connections, housing stability, food insecurity, stress, postpartum depression, and health literacy. Patients with a positive screen will meet with our clinical research coordinator to discuss their interest in enrollment. If the patient meets inclusion criteria and agrees to enrollment, they will be randomized to Doula enhanced care or routine care.
3. A flyer will be placed in the waiting room and clinic rooms at the University of Kansas Medical System.
4. Patients with a positive screen will meet with our research coordinator to discuss their interest in enrollment. If the patient meets inclusion criteria and agrees to enrollment, they will sign a consent form and be randomized to Doula enhanced care or routine care.

B. Screening Interview/questionnaire:

Black patients presenting to University of Kansas Health System Department of OBGYN for prenatal care will be screened using the "Social Determinants of Program Page Health" screening tool in Epic, the electronic medical record (EMR), utilized in the outpatient settings.

C. Informed consent process and timing of obtaining of consent:

- 1 Clinical Research Coordinator or Investigators will give potential participants comprehensive information about the study and obtain their written consent.

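### The depression and stress answers that can qualify a patient for entry are not carried into the postpartum depression comparison, so a likely prognostic baseline value goes unused (minor)

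*Combined protocol and SAP*

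**What the plan says.** **Entry.** The inclusion criteria (II.D.1.b) require "A positive social determinants of health screen". Recruitment (III.A.2) defines it: "Patients with one or more positive question in any of the following areas equals positive social determinants of health screen". Ten areas follow: tobacco use, alcohol use, and then "financial resource strain, transportation needs, social connections, housing stability, food insecurity, stress, postpartum depression, and health literacy". Depression and stress are thus two of ten possible routes into the trial. No exclusion criterion concerns depression.

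**Timing.** II.D.1.c states: "Patients must have an estimated gestational age of at least 14 weeks, but less than 28 weeks (27.6) when enrolled in the study". Patients are screened and found eligible before they are randomized, so the screen precedes both randomization and delivery.

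**Outcome.** The hypothesis (I.A.2) is that "Doula enhanced care will lower instances of cesarean delivery, preterm birth, and postpartum depression rates". Study Significance (I.B.3) names postpartum depression among the secondary outcomes. Under II.E.1, all postpartum patients are "screened for postpartum depression using the Edinburgh scale on the day of discharge and at 2 weeks following their delivery by a phone call". No cut-off is given, nor any rule for which of the two time points defines the outcome.

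**Data and analysis.** The chart-review list in II.E.1 names neither the entry screen nor a depression history, although its list of comorbidities is open-ended. Allocation is 1:1 with 20 per arm and no stratification factor is named (II.C.2). The analysis (V.A.1) is t-tests, chi-squared tests and simple logistic regression, with no covariate.

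**The concern.** The same construct appears at both ends of the trial: it can admit a patient, and it is compared between arms after delivery. Nothing in the plan connects the two measurements. A patient who qualified on the depression area and is positive on the Edinburgh scale after birth looks the same in the data set as one whose symptoms are new.

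Three things are at stake, all confined to one secondary outcome. First, an entry value that probably predicts the later result is not used to sharpen the comparison. Second, with 20 per arm, the number of entry positives can differ by chance, and the report would have no means of showing it. Third, a reader of the result could not say whether a difference reflects fewer new positives or less persistence. The last matters because Study Significance (I.B.3) presents this trial as the basis for a larger grant application.

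**Working it through.** The plan states no depression rate, effect size or power for this outcome, so there is no figure of its own to reproduce. The only inputs from the documents are 40 patients, 20 per arm, 1:1 (II.C.2). The rest are assumptions:

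- p, the share positive on the entry depression area: 0.20, 0.30 or 0.40.
- r1, the chance of a positive Edinburgh screen after delivery if positive at entry: 0.40 or 0.50.
- r0, the same chance if negative at entry: 0.10.

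**1. Overall postpartum positive rate.** m = p·r1 + (1 − p)·r0.
- Low end: 0.20 × 0.40 + 0.80 × 0.10 = 0.16.
- High end: 0.40 × 0.50 + 0.60 × 0.10 = 0.26.
- Over 40 patients this is about 6 to 10 positives in total (40 × 0.16 = 6.4; 40 × 0.26 = 10.4).

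**2. Share of postpartum positives who were positive at entry.** p·r1 / m.
- Low end: 0.08 / 0.16 = 0.50.
- High end: 0.20 / 0.26 = 0.77.

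**3. Chance imbalance.** Treat the entry positives in each arm as independent Binomial(20, p). The probability that the arms differ by 4 or more patients is:

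| p | Probability |
|---|---|
| 0.20 | 0.164 |
| 0.30 | 0.226 |
| 0.40 | 0.258 |

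With the total fixed at 8, 12 or 16 of 40 (hypergeometric), it is 0.235, 0.301 or 0.333. These are higher mainly because an even total forces an even difference, so 4 or more then means the same as 3 or more. The binomial figures average over even and odd totals.

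**4. Effect of an imbalance of 4.** Four of 20 is 0.20. The shift in the rate difference is 0.20 × (r1 − r0).
- r1 = 0.40: 0.20 × 0.30 = 6 points.
- r1 = 0.50: 0.20 × 0.40 = 8 points.

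**5. Compared with the noise already present.** The standard error of the difference is √(2m(1 − m)/20).
- m = 0.16: √(2 × 0.1344/20) = 0.116.
- m = 0.26: √(2 × 0.1924/20) = 0.139.

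So 6/11.6 = 0.52 and 8/13.9 = 0.58. Over all combinations of p and r1 the ratio runs from 0.46 to 0.66, which is about half a standard error.

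**6. Value of adjustment.** The correlation between the binary entry result and the binary outcome is phi = (r1 − r0)·√[p(1 − p)] / √[m(1 − m)].
- Low end (p = 0.20, r1 = 0.40): 0.30 × 0.400 / 0.367 = 0.33.
- High end (p = 0.40, r1 = 0.50): 0.40 × 0.490 / 0.439 = 0.45.

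The variance explained is phi², or 0.107 to 0.200. The effective sample size is 40/(1 − phi²):
- Low end: 40/0.893 = 44.8.
- High end: 40/0.800 = 50.0.

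Adjustment is therefore worth roughly 45 to 50 patients instead of 40. This is a linear approximation for a binary outcome. A logistic odds ratio does not gain precision in the same way.

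**The case against.** **Randomization already deals with it.** Entry positives are balanced in expectation, and chance imbalance is part of what the confidence interval covers. This stands. A reader might infer that selecting on depression biases the comparison between arms; 1:1 randomization rules that out. A shift of half a standard error is also too small to determine the result by itself.

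**Cases present at entry are counted as outcomes.** A reader might infer this too, but the documents do not say it. A positive screening answer is not a case. Such a patient contributes only if she is positive on the Edinburgh scale after delivery. With no case definition in the plan, the counting is inferred from silence. Depression is also only one of ten areas, so many patients may enter by another route.

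**Only new onset should count.** One could argue that persistent symptoms dilute a preventive effect. For example, if doula care halved new onset from 20% to 10% and left persistence unchanged, with 20% positive at entry and 50% to 90% of them persisting, the risk ratio would move from 0.50 to between 0.69 and 0.76. That rests on equal persistence in both arms, which the documents do not support. The hypothesis in I.A.2 concerns postpartum depression rates, not onset, and two prenatal doula visits could plausibly reduce persistence. The overall comparison is legitimate.

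**The entry answer may not exist for everyone.** III.A.2 requires one positive answer in any area; it does not say that every area is completed. It also labels the area postpartum depression although the screen is used during pregnancy, and it does not identify the questions asked. This stands: the covariate may be incomplete.

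**Little hangs on it.** This is one of four named secondary outcomes in a 40-patient trial. Under the illustrative 20% against 10%, power with 20 per arm is only 13.9% even with no entry positives. Adjustment would not make the comparison conclusive. That limits the weight of the point, but a cheap gain in precision is still worth taking.

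**Conclusion.** The point holds as a minor one. One positive answer on depression or stress is enough for entry, postpartum depression is a secondary outcome, and neither the listed chart-review items nor the planned analysis uses the entry result. The open comorbidity list does not prevent recording depression history, but the analysis would still be unadjusted.

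The consequences are modest loss of precision, an unseen chance imbalance, and a result that is harder to interpret. The primary survey outcome is untouched.

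Every rate behind the sizes given is assumed. The true number of entry positives is unknown, and would remain so if only the listed items were abstracted. That the entry answer predicts the later Edinburgh result is likely, but no figure in the documents establishes it.

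**What to change.** 1. Add the depression and stress results from the Epic eligibility screen to the REDCap baseline form, with a category for not answered, and tabulate them by arm.
2. Keep the overall postpartum Edinburgh comparison as the randomized secondary outcome, and adjust it for the entry depression result. Use linear adjustment if the score is analyzed. For a positive/negative outcome, use a risk difference or risk ratio stratified by entry result, because only about 6 to 10 positives are expected under the assumptions above.
3. Before analysis, state which Edinburgh time point and which definition of a positive screen the comparison uses.
4. Report, by arm and descriptively only, new positives among patients negative at entry and persistent positives among those positive at entry.

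The cost is one or two abstracted fields and one covariate, with no extra patient contact. The drawbacks are possible missing entry answers, which would reduce the gain, and subgroup counts too small for any test.

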 - d. Patients may have the following fetal anomalies and participate in the study, but these are not requirements for inclusion:
 - i. soft markers (including pyelectasis), intracardiac echogenic foci, mild ventriculomegaly, thickened nuchal fold, absent or hypoplastic nasal bone, isolated echogenic bowel, short long bones and polydactyl.
2. **Exclusion criteria:**
- a. Pregnancy not viable or pregnancy not intrauterine on ultrasound
 - b. Patients who are not willing to be randomized into not receiving doula enhanced
 - c. Patients who do not plan to delivery at the University of Kansas Health System
 - d. Non-Black birthing people.
 - e. Planned cesarean section
 - f. Patients with a known major fetal anomaly
 - g. Non-English speaking
3. Withdrawal/Termination criteria: Patients who transfer care to another facility or attend fewer than two prenatal appointments will be terminated from the study. Patients who wish to withdrawal may at any time.
4. Participants may participate in other studies at the same time.

E. Specific methods and techniques used throughout the study

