- 2 Clinical Research Coordinator or Investigator will speak directly to the patient either in person or via telephone to explain the study, Doula enhanced care, and discuss interest in enrollment. They will go through the consent form with them, answer questions to satisfaction of the patient, and provide a copy to the patient, as well as contact information should they have questions later
- 3 Only patients able to provide informed consent will be included in this study. Research Coordinator or Investigator will determine if patient is eligible to provide consent. If there is any question to the patient's capacity to give consent, they will consult with the medical team and PI.
- 4 If the PI is the physician responsible for providing direct patient care, to avoid coercion, the patient must be consented by the Clinical Research Coordinator or another Co-Investigator. The care team will not be notified of the patient's enrollment until they participate in study procedures in the office.

D. Alternatives to Participation:

1. Patients may seek Doula enhanced care independent of the study and can be referred to the consulting Doulas assisting in this study.

E. Costs to Subjects:

2. No cost to patient, the grant will pay for the Doula enhanced care.

F. How new information will be conveyed to the study subject and how it will be documented:

3. No new information will be presented to the participants throughout the study. Surveys will be conducted both in person and via phone. Participants answers will be recorded in RedCap.

G. Payment, including a prorated plan for payment:

N/A, part of routine pregnancy care

Payment for a research-related injury:

N/A, part of routine pregnancy care

IV. Data Collection and Protection**A. Data Management and Security:**

1. Participant information will be de-identified by the Clinical Research Coordinator, who will assign an alphanumerical study ID to the patient. Only the Clinical Research Coordinator and PI will have access to identifiable information, which will be stored securely in Redcap and CRIS/Velos systems.
2. All collected data will be stored securely in Redcap or CRIS/Velos systems. There will be no paper source.
3. Subjects will only be identified by an alphanumerical study ID assigned by the Research Coordinator when the survey is conducted.
4. Clinical Research Coordinator and PI will maintain and have access to the key to the assigned groups.

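### Eligibility does not address patients who already have a doula, and no doula-exposure item is described for either arm, so a null result could not be interpreted

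*Combined protocol and SAP*

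**What the plan says.** II.A and V.B set the primary objective, which is to "demonstrate improved perceived communication and quality of maternal care among Black birthing people with Doula enhanced care compared to routine pregnancy care". Twenty patients per arm are randomised 1:1 (II.C.2). Under II.E.1 the routine-care arm "will continue to receive routine prenatal care at The University of Kansas and routine pregnancy care during the labor and delivery hospitalization"; nothing is said about doulas in that arm. The doula arm is to have two prenatal visits, attendance at labor and delivery, and at least one postpartum visit.

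The only eligibility criterion that touches doula use is exclusion b in II.D.2: "Patients who are not willing to be randomized into not receiving doula enhanced". The withdrawal rule in II.D.3 concerns transfer and attendance only: "Patients who transfer care to another facility or attend fewer than two prenatal appointments will be terminated from the study".

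On data, II.E.1 states: "A chart review will be performed to obtain maternal demographic information and secondary outcomes including maternal age, gravity/parity, gestational age at delivery", and goes on to delivery, comorbidity, labor-complication and breastfeeding items. Of the survey it says: "Questions will aim to evaluate healthcare communication and perceived quality and respectfulness of care".

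III.D, headed Alternatives to Participation, consists of one sentence: "Patients may seek Doula enhanced care independent of the study and can be referred to the consulting Doulas assisting in this study".

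V.A plans t-tests and chi-squared tests. It names no analysis set and does not mention crossover or delivery of the intervention.

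**The concern.** Three silences combine. A patient who has a doula at enrollment, and is willing to be randomised, is eligible. A routine-care patient may obtain a doula after randomisation: doula care is explained to every candidate at consent (III.C.2), enrollment falls between 14 and under 28 weeks (II.D.1), and III.D does not say whether its referral route ends at randomisation. And no described data item would show that either had happened.

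The same gap covers the doula arm. Attendance at the birth depends on the doula being notified at admission, and the number of postpartum visits has a floor but no fixed value, so the dose actually delivered can vary without being recorded.

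At stake is what the result can be used for. I.B.3 presents the study as the step before an R01 proposal. If the arms look alike, that proposal needs to know whether the program did not help, whether controls had doulas, or whether the planned visits did not take place. Each points to a different next study.

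**Working it through.** **Step 1: the eligibility text.** Read against the question of whether a patient who already has a doula can be randomised, exclusions a to g cover viability, unwillingness to be randomised to no doula, place of delivery, race, planned cesarean, major fetal anomaly and language. Only b is close. It tests willingness at enrollment, not current or arranged doula use. Such a patient is not excluded.

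**Step 2: the data items.** The chart-review list and the survey description in II.E.1 name no outside doula contact, no count or date of study-doula visits and no presence at the birth. The list is introduced as inclusive and the survey is not reproduced, so the supportable statement is that no exposure item is described.

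**Step 3: the plan's own figure.** The total of 40 (II.C.2) cannot be reproduced, because no effect size, standard deviation, event rate, alpha, power or dropout is stated. What follows is illustration, not a correction of that figure.

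**Step 4: dilution.** Let Δ be the full effect of doula care and c the share of routine-care patients who receive all of it. The control mean moves from μ to μ + cΔ while the doula-arm mean stays at μ + Δ, so

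as-randomised difference = (μ + Δ) − (μ + cΔ) = (1 − c)Δ.

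The sample size giving the same power without crossover is 40(1 − c)². The documents give no value for c. Assumed values, with t-test power at 20 per arm and an assumed two-sided alpha of 0.05:

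| Controls with a doula | c | Effect left | 40(1 − c)² | Power, d = 0.91 | Power, d = 0.5 |
|---|---|---|---|---|---|
| 0 of 20 | 0 | 100% | 40 | 80% | 34% |
| 2 of 20 | 0.10 | 90% | 40 × 0.81 = 32.4 | 71% | 28% |
| 4 of 20 | 0.20 | 80% | 40 × 0.64 = 25.6 | 61% | 23% |
| 6 of 20 | 0.30 | 70% | 40 × 0.49 = 19.6 | 50% | 19% |

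Here d is the standardised difference; 0.91 is the value that 20 per arm detects with 80% power. Each exposed control is 1/20 = 5% of the arm.

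**Step 5: why exposure must be recorded.** Let m be the share of the doula arm who receive none of the effect because visits were not delivered. The difference is then (1 − m)Δ − cΔ = (1 − c − m)Δ. With c = 0.20 and m = 0 it is 0.80Δ; with c = 0 and m = 0.20 it is also 0.80Δ; and a true effect 20% smaller with c = m = 0 gives the same number. The outcome data alone cannot tell these apart.

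**The case against.** The strongest reply is that the text shows a possibility and little more. III.D stands under a heading about what patients can do instead of joining, and most naturally addresses decliners. A reader might infer that the plan sends routine-care patients to the trial's own doulas; no section does so. A reader might also infer that the comparator is the absence of a doula. The objective says routine pregnancy care, and a doula whom a control finds for herself can be regarded as part of that. Both points stand, and they rule out calling such use a breach of the protocol.

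The rate may also be low. I.C.1 says that access barriers often keep the most vulnerable patients from doula care, eligibility requires a positive social-determinants screen (though that screen also counts non-financial items), the documents mention payment only for the study's doula care, and exclusion b removes patients unwilling to go without a doula. This stands as a reason to expect a small c. It does not show that c is zero, and the described data could not show it either.

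The survey's four open-ended questions might bring a doula to light, and the REDCap tool was still to be built. So it would be too strong to say that exposure is certain to go unseen. A chance mention is not systematic capture, however.

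Finally, Step 4 gives every exposed control the full effect on every outcome. That is the upper end for a given c; a doula present only at labor, for example, could not change preterm birth. And since no power target is stated for 40 patients, the power figures describe sensitivity, not a missed target.

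**Conclusion.** The point holds in limited form. As written, the plan can randomise a patient who already has a doula, describes no item that would record doula exposure in either arm, and leaves open whether the III.D referral extends to routine-care participants. Any crossover pulls the as-randomised difference toward zero by the factor (1 − c): to 90%, 80% and 70% for an assumed 2, 4 and 6 of 20 controls, on the assumption that each receives the full effect. The true rate is unknown and may be small.

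The firmer part does not depend on c. With no exposure data, a null result cannot be separated into an ineffective program, exposed controls and undelivered visits. Exposure fields are worth having even if crossover turns out to be nil, because only they could show it. The documents do not support the stronger reading that the design channels controls to the intervention. This is a worthwhile, inexpensive improvement and not a defect that invalidates the comparison.

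**What to change.** 1. **II.D.2:** add an exclusion for a patient who already has or has arranged a doula for this pregnancy.
2. **II.E.1 and the REDCap tool:** in both arms, record any doula contact, its source, and whether it was prenatal, during labor or postpartum. In the doula arm, also record each completed visit with its date, and whether the doula was present at the birth. A question at the existing postpartum survey can supply the contact data.
3. **V.A:** state that the as-randomised comparison is the main result and that doula exposure will be reported by arm beside it.
4. **III.D:** reconcile it with the randomised comparison by stating whether it applies only to patients who do not enrol. Patients remain free to seek a doula themselves.

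The cost is amendment wording, a few data fields and one survey question. The downside is that a few patients who already have doulas are not enrolled, which may slow recruitment slightly and narrows the population to those without an existing doula.
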